Available information suggests that there are 3 predominant microbe enterotypes described initially in 2011 (20). Studies in 5 subjects consuming either a high fat/low fiber or a low fat/high fiber diet in a single study suggested that the distinct differences between individual subjects generally were maintained over 10 days after an abrupt change in the 1st 24 hours. No switching in the primary 3 enterotypes was detected within 1 week of the diets (21).

In a study of Malawi twins, discordant for kwashiorkor, administration of a therapeutic food supplement resulted in modest but non significant changes in the fecal microbiota in 2 weeks (22).

A much quoted study by Faith et al evaluated the stability of the fecal microbiome up to 5 years showing that up to 60% of the individual species remained stable (23). However, weight loss impaired microbiota stability in studies performed before and after 8 weeks of a low calorie diet.

In our present studies, we had taken fecal samples 2-3 days after the RUH admission and the start of a diet designed by our Bionutrition Department that mimicked each subject's pre-study diet and then initiated the intervention. However, on the basis of the available information, we do not know how long to administer such a diet before taking the initial fecal sample prior to the medical intervention such as Celecoxib. The present proposed study will determine whether the fecal microbiota is stable after 3 or 7 days or needs 14 or more days. This information will guide our procedures in future similar studies.

12.2 * Engaging Stakeholders: Describe any plans to engage other stakeholders (Scientists, practitioners, patients, advocacy groups, etc.) for hypothesis generation, or feasibility purposes.

[name] who will perform several analyses of adipose tissue pertaining to effects of Celecoxib on the aromatase enzyme. [name] and [name] who will perform microbiome studies that aim to determine whether Celecoxib alters fecal microbiota composition and whether a self-selected diet mimicking a subject's pre-study long-term diet will keep fecal microbiota composition constant.

12.3 * Hypothesis

Describe the **research hypothesis** in a single sentence.

Celecoxib, an inhibitor of cyclooxygenase-2 (COX-2) will reduce urinary excretion of PGE-M, and suppress levels of prostaglandin E₂ (PGE₂) and aromatase in inflamed abdominal subcutaneous adipose tissue in grade 2-3 obese postmenopausal women.

12.4 * Aim(s)

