The sequence data will be screened and filtered using Mothur before each sequence is classified using a modified inhouse database containing sequences from GreenGenes 99 and retrieved 16S sequences from Genbank. The relative abundance of the microbiota will be represented by the percentages of the classified taxa sequences out of the total sequences present in the sample. In addition to the classification of the raw sequences, sequences that fall into an operation taxonomic unit (OTU) with 97% similarity will also be classified.

Additionally, the biodiversity of the microbiota of a sample will be surveyed using the Shannon Diversity Index. The comparison of the biodiversity between samples will be measured by unweighted UNIFRAC distances and visually represented by the Principal Components Analysis. A LDA Effect Size (LEfSe) analysis can be completed to look for specific bacteria that may contribute to any differences seen between groups of samples.

12.8 * Data Analysis

Describe method(s) of data analysis. Include the role of external collaborators as appropriate.

With 10 subjects, we will be able to detect effect sizes larger than 1 with 80% power at 0.05 significance level on a 2-tail test

12.9 * Explain the rationale for the choice of statistical measures and the number of subjects proposed for the study, including the power calculations when applicable.

In a study including women across the BMI spectrum, the effect size for the pre vs post differences in PGE-M excretion was found to be 0.64 for current smokers, 1.06 for former smokers and 0.68 for non-smokers (17).

Mice data shows that baseline levels of PGE-M are twice as high in obese than lean mice and the reduction on PGE-M is 70% higher in obese mice. Based on this, we will power our study to detect an effect size of 1 in the decrease of PGE-M levels with treatment. Studies in obese mice have shown an almost 3-fold increase in excretion of PGE-M compared to lean mice ([name] unpublished observations).

To test if the measurement of PGE-M in the urine will decrease after administration of Celecoxib 200 mg BID a paired t-test will be used.

A similar approach will be used to test the secondary outcomes including PGE-2 in adipose tissue, cytokine levels (log-transformed), and estrogen metabolites. Decrease in outcomes will be correlated to identify which variable correlates with the primary outcome.

12.10 * Will samples be coded?

Yes No

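### The only between-sample distance named for the stool analysis (12.7) ignores relative abundance and has no stated common read depth; add an abundance-weighted distance beside it

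*Combined protocol and SAP*

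**What the plan says.** The microbiota methods are in section 12.7, under the methodology for stool specimens. They list four outputs.

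- Relative abundance: "The relative abundance of the microbiota will be represented by the percentages of the classified taxa sequences", as a share of all sequences in the sample. No comparison between samples is attached.
- Within-sample diversity: "the biodiversity of the microbiota of a sample will be surveyed using the Shannon Diversity Index".
- Between-sample comparison: "The comparison of the biodiversity between samples will be measured by unweighted UNIFRAC distances and visually represented by the Principal Components Analysis".
- Taxon-level follow-up: "A LDA Effect Size (LEfSe) analysis can be completed to look for specific bacteria that may contribute to any differences seen between groups of samples".

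On processing, "The sequence data will be screened and filtered using Mothur" before classification. No common read depth, rarefaction or minimum read count is given.

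Two questions depend on these outputs. Section 12.6 lists the time needed to reach stable fecal flora as a secondary outcome, and section 12.1 asks whether 3, 7, or 14 or more days are needed. Section 12.2 says that the microbiome studies "aim to determine whether Celecoxib alters fecal microbiota composition". Section 12.1 gives the background partly in terms of predominant enterotypes and partly in terms of how many species persist over time.

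**The concern.** Both questions compare samples from the same woman at different times, and section 12.7 names one distance for comparing samples. That distance discards abundance. If a woman's dominant taxa change rank but every taxon stays detectable, the distance sees almost nothing. A reader relying on it could conclude that the flora had settled, or that celecoxib had left composition unchanged.

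A second, separate issue acts the other way. Detection of rare taxa depends on how many reads a sample receives. Two samples of one unchanged community, read at different depths, look further apart than two read equally. That could suggest instability or a drug effect where there is none.

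For the stability question, five women are admitted 11 days early, and section 12.1 says the answer will guide procedures in later studies.

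**Working it through.** **Inputs.** The documents give no read counts, taxon data or numerical microbiota target, so there is no microbiota figure to reproduce. The plan's one power statement (80% for PGE-M with 10 women at effect size 1) reproduces at 80.3% with the exact paired t-test, but has no bearing here. The communities below are assumed.

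**Formulas.** For branch *b* of length *l*, with *p* and *q* the shares of reads below it in the two samples:

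- Unweighted UniFrac = Σ *l* over branches present in exactly one sample ÷ Σ *l* over branches present in either.
- Weighted UniFrac (normalised) = Σ *l*·|*p* − *q*| ÷ Σ *l*·(*p* + *q*).
- Bray-Curtis = ½ Σ |*p* − *q*| over taxa.
- Shannon = −Σ *p* ln *p* over taxa.

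**Step 1: an exact case.** Take 128 taxa on a balanced tree with equal branch lengths (7 levels). Two taxa in opposite halves hold 60% and 5%; the other 126 share 35% equally. Let the two swap, to 5% and 60%.

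- Unweighted: every branch is present in both samples, so the distance is 0.
- Weighted: each level contributes 0.55 + 0.55 = 1.10 to the numerator and 2 to the denominator, so (7 × 1.10) ÷ (7 × 2) = 0.55.
- Bray-Curtis: 1.10 ÷ 2 = 0.55.
- Shannon: 2.516 before and after, since the same shares are held by different taxa.

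If instead the two taxa move to 32.5% each, unweighted is still 0, weighted is (0.275 + 0.275) ÷ 2 = 0.275, and Shannon rises from 2.52 to 2.79.

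**Step 2: with sampling noise.** Take 200 taxa, random coalescent trees, lognormal abundances (log-SD 2.2) and 10,000 reads per sample. Halve the two commonest taxa and double the next two. Two sets of simulations gave these means:

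| | Unchanged | Shifted |
|---|---|---|
| Unweighted, set A | 0.029 | 0.031 |
| Unweighted, set B | 0.033 | 0.033 |
| Weighted, set A | 0.008 | 0.074 |
| Weighted, set B | 0.008 | 0.085 |

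Unweighted UniFrac stays at noise level. Weighted UniFrac rises about nine- to eleven-fold (0.074 ÷ 0.008 ≈ 9; 0.085 ÷ 0.008 ≈ 11).

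**Step 3: would the other outputs show it?** In the Step 2 scenario the commonest taxon falls from about 26% to 15%. Shannon moves by 0.17 to 0.22 on average, against resampling noise of about 0.02. Both would usually show this shift if someone looked. Step 1 shows that Shannon alone is not a guarantee.

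**Step 4: unequal depth, unchanged community.** The fair comparator is two samples at the shallower depth, because equalising depth would bring both there.

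- 200-taxon communities: unweighted 0.070 at 3,000 v 30,000 reads against 0.055 at 3,000 v 3,000, a ratio of about 1.27. A second set gave 0.065 against 0.052, a ratio of 1.25.
- Three 128-taxon communities (log-SD 2.5): at 2,000 v 10,000 against 2,000 v 2,000, the ratios are 0.154 ÷ 0.149 = 1.03, 0.195 ÷ 0.183 = 1.07 and 0.172 ÷ 0.168 = 1.02.

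The mismatch therefore added between about 2% and about a quarter, depending on the assumed depths and community.

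**The case against.** The strongest reply is that UniFrac is not the whole analysis. A reader might infer from the single named distance that samples are compared by it alone, and that a large shift in dominant taxa would therefore pass unseen. The documents do not support that. Section 12.7 also produces taxon percentages, a Shannon index and possibly LEfSe, all of which use abundance, and Step 3 shows that the first two would normally reveal a shift of the size simulated. Nor does any section say that stability or the celecoxib question will be decided on UniFrac. No decision rule is given at all, which is arguably the more basic gap, and changing the metric does not fill it.

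This reply limits the point but does not remove it. The percentages and Shannon have no planned between-sample comparison. LEfSe is optional and contrasts groups of samples, so it does not measure how far one woman's flora has moved.

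A second reply is that presence or absence is a legitimate notion of stability: section 12.1 cites work on the share of species that persist. That stands, and it is why unweighted UniFrac should be kept.

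A third is that an application form may leave read depth to the laboratory's pipeline. Also fair: silence does not show that depth would go uncontrolled. It shows only that the plan does not fix it.

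**Conclusion.** The point holds in a limited form. The one distance named in 12.7 cannot register a change in abundance without gain or loss of taxa: it is exactly 0 in the worked case and at noise level in simulation, where weighted UniFrac rises about nine- to eleven-fold. The other outputs may show the change, but the plan does not commit to comparing them between samples.

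The depth effect is separate and modest, about a quarter at an assumed ten-fold imbalance and less in other runs. Two stronger readings should be resisted. Uneven depth does not help a real change pass as stable; it inflates distance, so the error is false instability or a false drug effect. Nor does it double the noise: that impression comes from comparing 3,000 v 30,000 reads with 10,000 v 10,000, and most of the gap is shallow sampling, which equalising depth would not remove.

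The reference to Principal Components Analysis, where principal coordinates would be usual for a distance matrix, is a matter of labelling. All sizes rest on assumed communities and depths. A secondary outcome and the celecoxib-microbiota question in a pilot are affected; the primary PGE-M analysis is untouched.

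**What to change.** In section 12.7, state that samples will be brought to one common read depth before any distance is computed. Then add weighted UniFrac or Bray-Curtis as a within-woman distance, reported alongside unweighted UniFrac for two purposes:

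- time to stability, across the pre-drug samples of the five early-admitted women;
- change from the pre-celecoxib sample to the on-celecoxib sample.

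The addition uses the same stool samples and sequences, so it costs wording and a little computing. The drawbacks are a second metric to report, which may disagree with the first, and the loss of some reads from the deeper samples.

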The use of NSAIDs has been associated with a reduced risk and spread of colorectal cancer. Most epidemiological studies suggest that use of NSAIDs also is associated with a reduced risk and spread of breast cancer although the protective effects are more modest. We speculate that this class of medication like others will be effective in some but not all individuals to reduce breast cancer risk. In particular, we hypothesize that these agents will be of benefit if used chronically in the up to 75% of obese postmenopausal women who demonstrate white adipose tissue inflammation and CLS. If Celecoxib suppresses levels of inflammation and aromatase in abdominal white adipose tissue which is likely to mirror what occurs in breast white adipose tissue, this would suggest that chronic use of NSAIDs is likely to reduce the risk and spread of hormone receptor-positive breast cancer in this growing segment of the population. Importantly, if reduction in urinary PGE-M reflects reduction in adipose tissue inflammation this would be a useful non-invasive marker for this property in future studies.

We additionally plan to study the fecal microbiota of 5 of the 10 participants being studied.

Studies on metabolic diseases such as obesity during the past few years have included important consideration of the impact of changes in the colonic microbiome. Indeed, several of our recent studies at The Rockefeller University Hospital have included a collection and storage of fecal specimens for later analysis. We, in collaboration with [name] at Cornell have established a relationship with [name] at MSKCC who is willing to perform analysis on specimens that were collected immediately before and after 10% weight loss in obese volunteers (PHO 785).

Our metabolic studies usually have been performed in small groups of subjects who are studied while consuming a preselected diet before and after an intervention.

As we plan similar studies, it has become evident that we do not know how soon after admission to RU and initiating a Bionutrition Department provided diet should fecal specimen collection be initiated as a stable baseline before starting the intervention. Previously, we only have used 3 days before the intervention based on scant data in the literature. We now believe that it is very important to determine how long it takes under the condition of our studies at RUH to establish reasonable fecal microbiota stability.

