5 out of the 10 participants recruited will be asked to be admitted to the Rockefeller University Hospital IPU 11 days earlier (2 weeks prior to Celecoxib administration) for a total of 24 inpatient days in order to determine stabilization time for fecal microbiota. 4 additional stool samples will be collected at Days 0,3, 7, and 11, +/- 1 day.

Screening Visit #1

Informed consent

Medical History and Physical exam

EKG

Waist measurement

Distribution of 3-day food diary

HIV POCT

Subjects will be instructed to fast 10 hours prior to their next visit for fasting labs.

Subjects will be instructed to discontinue taking over the counter medications (OTCs). Those subjects which require medication for relief of pain will be advised to use only Tylenol and given a week's supply.

Screening visit #2

Return of 3 day food diary

Fasting labs to include- CBC/Diff, ESR, Comprehensive Metabolic Panel, Thyroid Stimulating Hormone, lipid profile, hsCRP, PT/PTT/INR, serum estradiol

Bionutrition consult to review the 3 day food diary and determine subject's "usual diet"

A clinic meal will be provided after labs are drawn.

Dispense Tylenol 325 mg #30, 2 tablets by mouth as needed for pain.

Eligibility will be determined following lab results. Subjects will be scheduled for admission within 1-4 weeks of their screening. If greater than 1 month has passed from screening, safety labs (CBC/DIFF, CMP, PT/PTT/INR) will be re-drawn prior to admission.

Inpatient Admission

Day 0

Admit to RUH at approximately 11 AM

Study diet lunch and dinner

Day 1

Usual diet

Day 2

Spot urine for PGE-M

24 hour urine for testing of the following: PGE-M, estrogen metabolites, creatinine, volume stool sample +/- 1 day

NPO after 9 pm except water

Day 3

Fasting research labs- TNF- α , IL6, IL8, MCP-1, insulin, serum estradiol and estrogen metabolites, serum endocannabinoids

MSKCC labs: CBC, ESR, CMP, hsCRP, PT/PTT/INR, lipid panel, estradiol

Spot urine for PGE-M after completion of 24-hr urine collection

Fat biopsy

Start Celecoxib 200 mg PO BID

NPO after 9 pm except water

Day 4

Bod Pod

Continue Celecoxib 200 mg PO BID

Day 5

Usual diet

Continue Celecoxib 200 mg PO BID

Day 6

Usual diet

Continue Celecoxib 200 mg PO BID

Day 7

Usual diet

Continue Celecoxib 200 mg PO BID

Day 8

Usual diet

Continue Celecoxib 200 mg PO BID

Day 9

Usual diet

Continue Celecoxib 200 mg PO BID

Day 10

Usual diet

Continue Celecoxib 200mgPO BID

Day 11

Usual diet

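### The only test named for the microbiota (LEfSe, optional, groups undefined) is unpaired in its standard form, although both microbiota questions are within-woman; the power loss depends on a correlation the plan does not give

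*Combined protocol and SAP*

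**What the plan says.** **Questions.** Section 12.6 lists the time needed for the fecal microbiota to become stable as a secondary outcome. Section 12.2 adds that the microbiome collaborators "aim to determine whether Celecoxib alters fecal microbiota composition". Both ask about change over time in the same woman.

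**Samples.** Section 12.1 states: "We additionally plan to study the fecal microbiota of 5 of the 10 participants being studied". For these five early-admission women, Section 12.7 says "4 additional stool samples will be collected at Days 0,3, 7, and 11, +/- 1 day". With the Day 14, Day 23 and end-of-study samples, that makes seven per woman. The standard schedule also collects stool, on Day 2 ("creatinine, volume stool sample +/- 1 day"), on Day 12 and at the end-of-study visit, which makes three per woman.

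**Methods.** Section 12.7 describes relative abundance and the Shannon index. Differences between samples are "measured by unweighted UNIFRAC distances and visually represented by the Principal Components Analysis". No test is attached to any of these. The one inferential tool is LEfSe, "A LDA Effect Size (LEfSe) analysis can be completed to look for specific bacteria", namely those "that may contribute to any differences seen between groups of samples". The groups are not defined, and no pairing, block or subject term is mentioned.

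**Elsewhere.** Section 12.9 names a paired t-test for urinary PGE-M and a like method for secondary outcomes, giving adipose PGE-2, cytokines and estrogen metabolites as examples. The microbiota is not among the examples.

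**The concern.** The documents do not describe the test inside LEfSe. In its standard form, the first screen is a Kruskal-Wallis comparison of groups of samples, which has no place for the woman a sample came from. Stable differences between women then count as noise, and a consistent shift within each woman can be hidden by them. Section 12.1 reports, from a cited five-subject diet study, that "the distinct differences between individual subjects generally were maintained over 10 days". That is the setting in which an unpaired test is weak for within-person change.

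For stability, low power pushes the answer one way. A test that cannot see a shift between Day 0 and later days makes the microbiota look settled early. Section 12.1 says the finding will guide later studies, so a false conclusion of early stability would carry forward. For celecoxib, a real change in a taxon could be missed.

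**Working it through.** **1. The plan's own power figure.** Section 12.8 gives 80% power for 10 subjects, effect size 1, two-sided 0.05. For a paired t-test the noncentrality is 1 × √10 = 3.16 on 9 degrees of freedom, and the power is 80.3%. The figure reproduces, but it belongs to PGE-M. No power, variance or effect size is given for the microbiota.

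**2. What the unpaired test sees.** Take total variance 1, with share ICC between women.
- Within-woman SD of one sample: √(1 − ICC).
- SD of a before/after difference: √(2(1 − ICC)).
- A within-woman effect of 1 is therefore a shift of √(2(1 − ICC)). This is also the standardised difference seen by a test that ignores the woman: 1.41, 1.18, 1.00, 0.77 and 0.45 at ICC 0, 0.3, 0.5, 0.7 and 0.9.

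The paired effect stays at 1 while the unpaired one shrinks as the ICC rises.

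**3. Power, before versus on drug.** This is by simulation with normal data, one taxon, two-sided 0.05 and no multiplicity. Only the Kruskal-Wallis screen was modelled, not the LDA step. ICC and effect size are assumptions. Repeat runs differed by up to about 3 points.

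| ICC | Unpaired, 10 women | Unpaired, 5 women |
|---|---|---|
| 0 | 85% | 50% |
| 0.3 | 73% | 37% |
| 0.5 | 55% | 26% |
| 0.7 | 34% | 14% |
| 0.9 | 4% | 2.5% |

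At every ICC, the paired tests with ten women give about 78-80% (signed-rank) and 80-81% (paired t). With five women the paired t gives about 40%.

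In one run with ten women, the share of paired-t power lost was:
- ICC 0.3: 1 − 72.2/80.9 = 11%
- ICC 0.5: 1 − 57.3/80.4 = 29%
- ICC 0.7: 1 − 33.8/81.0 = 58%
- ICC 0.9: 1 − 3.7/80.6 = 95%

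**4. Power, stability.** Five women, five pre-drug days (0, 3, 7, 11, 14), Day 0 shifted by 2 within-woman SDs (assumed).

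| ICC | Kruskal-Wallis | Friedman | Repeated-measures ANOVA |
|---|---|---|---|
| 0 | 69% | 56% | 81% |
| 0.3 | 47% | 57% | 81% |
| 0.5 | 30% | 56% | 81% |
| 0.7 | 13% | 57% | 79% |
| 0.9 | 1% | 55% | 80% |

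A permutation test restricted within woman gave 78-80% at ICC 0.5 to 0.9.

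**5. Limit on the paired rank test.** With five women, the smallest two-sided exact signed-rank p-value is 2/2⁵ = 0.0625, so pairwise signed-rank tests between days can never reach 0.05. With ten women it is 2/2¹⁰ = 0.00195.

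**The case against.** **LEfSe is optional and its groups are undefined, so the plan does not commit to an unpaired comparison.** This is true. But if LEfSe is not run, Section 12.7 names no microbiota test at all. Either way a within-woman analysis has to be specified.

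**Section 12.9 may already extend paired testing to the microbiota.** Stability is a secondary outcome and the examples there are not exhaustive, so the reading is possible. The text does not say it, however, and a before/after t-test does not define time to stability over five days. UniFrac distances can be taken between two samples of one woman, but no test is attached to them.

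**The ICC and effect size are assumed.** This stands. The evidence in Section 12.1 is qualitative, comes from five subjects, and follows an abrupt change in the first 24 hours. The effect of 1 is borrowed from PGE-M. For a within-woman effect of 2 with ten women, unpaired power is still 97% at ICC 0.7 and falls to 50% at 0.9.

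**Multiplicity shrinks the gain.** This stands in part. With the floor of 0.00195, a single changed taxon survives Benjamini-Hochberg at 0.05 only if at most 0.05/0.00195 ≈ 25 taxa are tested. At effect 1, the chance that a taxon reaches that floor is about 0.841¹⁰ = 18%. So 78-80% is not the power of the adjusted analysis. A stricter threshold lowers both tests, though, and at 0.005 the paired test stays ahead from ICC 0.3 upward.

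**Stronger readings a reader might infer.** One is that LEfSe loses most of its power whatever the data. The documents give no ICC, and at effect 1 that holds only from about 0.65 upward. Another is that pooling repeats would inflate false positives. That needs a comparison between groups of women, and none is planned. For within-woman comparisons the unpaired test is conservative: its null rejection rate with ten women was 4.7%, 1.5% and 0.3% at ICC 0, 0.5 and 0.7.

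**Conclusion.** The point holds in a conditional form. The only inferential method named for the microbiota is, in its standard form, unpaired, while both questions are within-woman and each woman gives three or seven samples. With ten women, effect 1 and one taxon, the loss against a paired t-test is about 11% of its power at ICC 0.3, 29% at 0.5, 58% at 0.7 and 95% at 0.9. At ICC 0 there is no loss and the unpaired test is slightly ahead. Section 12.1 makes the upper part of that range plausible but does not establish it.

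The primary PGE-M analysis is unaffected. Stability is a listed secondary outcome. The celecoxib effect on the microbiota appears only in Section 12.2 and is exploratory. The change is worth making because a better analysis of the same samples is available at almost no cost.

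**What to change.** - **Before versus on celecoxib.** Test each taxon's within-woman change with a paired test over all women who have both samples, adjust for false discovery, and report as exploratory. Confirm whether this covers all ten women, since Section 12.1 speaks of five while the standard schedule also collects stool. If more than about 25 taxa are tested, prefer a paired t-test on transformed abundance or shorten the list of taxa, because of the signed-rank floor.
- **Stability in the five early-admission women.** Analyse all pre-drug days jointly with woman as a block, by a mixed model or a permutation test restricted within woman. Use the same restriction for UniFrac distances. Do not use pairwise signed-rank tests. The Day 14 sample has a one-day window and celecoxib starts that day, so count it as pre-drug only if it was taken before the first dose.
- **Interpretation.** State that a non-significant result is not evidence of stability or of no drug effect. Even the paired t-test has only about 40% power with five women at effect 1.

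**Cost.** Some analysis code and a few sentences, with no new data. If within-woman correlation is near zero, the paired test has slightly less power than the unpaired one (about 80% against 83-85% with ten women).
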